Patients will be screened for eligibility, consented, and enrolled during their electrophysiology clinic appointment (standard of care) preceding their scheduled ablation. Based on prior experience with high dose IV ascorbic acid and the study focus on inflammatory effects, a limited list of exclusion criteria will include: diabetes mellitus with poor control or requiring insulin therapy (due to concerns that the infusions may interfere with glucometer readings), active renal calculus, active acute or chronic infection (including HIV and hepatitis C), active or recent (within 5 years) malignancy, autoimmune or auto-inflammatory disease, and recent or active use of immunosuppressive medications.

Upon admission for their ablation (standard of care), subjects will begin the first study infusion (sterile L-ascorbic acid diluted in 50mL of 5% dextrose in water or matched placebo of 50mL 5% dextrose in water). Once the subject has demonstrated no adverse effects of the first infusion, the AF ablation will proceed as scheduled. Patients will continue receiving infusions every six hours (+/- 3 hours) for a total of four infusions (research intervention). Of note, this 24 hours' worth of infusions was chosen as opposed to the 4 days' worth of infusions which was approved under the original IND (attached), since patients who are undergoing routine AF ablations rarely stay in the hospital longer than 24 hours. The shorter duration of infusions is still expected to test the theoretical benefit, while exposing the patients to even less risk of adverse reactions to the study agent than the 4 days' worth of infusions that are granted under the IND.

Prior to the first infusion, blood samples will be taken to measure plasma levels of ascorbic acid, biomarkers of inflammation (high-sensitivity C-reactive protein [hsCRP], interleukin-6 [IL-6]), and markers of blood vessel damage (von Willebrand Factor [vWF]), all part of the research intervention. A basic metabolic profile will be measured prior to the first infusion (standard of care), followed by measures of kidney function at 24 hours (+/- 12 hours) and at 30-day (+/- 14 days) follow up visit (research labs).

Patients will be monitored during their admission and during their follow up visit for any changes in blood pressure or heart rate, or any other reaction felt to be potentially related to the ablation procedure; monitoring for these elements in the history/physical

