Disease-specific concerns related to the infusions include: interference with point of care glucometer readings (resulting in falsely high results), which is not seen in venous laboratory glucometer readings. In large doses of vitamin C, hyperoxaluria can be observed in 1-10% of patients, raising concerns primarily for patients with active renal calculus or those prone to recurrent renal calculi. Studies involving patients with advanced cancer have reported infrequent side effects consisting of nausea, vomiting, dizziness, and headache.

Other potential risks of participating in the research study include the mild risks of blood draws (bleeding, infection, damage to soft tissue). To minimize this, research-related blood draws will be taken from existing intravenous catheters placed for standard of care purposes (if applicable) or combined with clinically-indicated lab draws to avoid repeat phlebotomy.

2 * Describe how the risks / harms will be minimized:

Diabetics will be excluded if they are on insulin therapy and/or if they have uncontrolled diabetes, defined as a glycosylated hemoglobin of greater than or equal to 8%. While admitted periprocedurally, signs will be posted inside and outside of the patient rooms as a warning that point of care glucose readings should not be considered reliable within 36 hours of the infusion, in case this is ordered clinically. In-services will be given to the nursing staff in all involved clinical areas to educate them on the effect of high dose ascorbic acid infusions on point of care glucometers.

Patients with active renal calculus or those deemed prone to recurrent renal calculi will be excluded from the study.

Below is our protocol for addressing the blood glucose monitoring concerns:

Guidance for blood glucose monitoring in patients enrolled in investigational Vitamin C Studies under this IND:

Glucose levels in this study population are checked daily as standard of care, and point of care testing is not usually needed. However, all studies under this IND follow the glucose monitoring plan outlined below. If additional glucose draws are required for a participant in this study, all additional draws outside of standard of care will be billed to the study. Additional glucose draws, if needed, will be determined on an as needed basis by the clinical team.

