Ascorbic acid is known to artefactually raise POC blood glucose readings; however, it does not raise blood glucose readings from a basic metabolic panel or glucose results using the gas lab. Thus, extreme care must be taken to assure an accurate blood glucose level from a metabolic laboratory (BMP) or arterial blood gas panel before initiating any insulin therapy, including sliding scale or scheduled insulin.

Guidance for blood glucose monitoring in patients enrolled this study:

◆ Critical care Nursing and Physician leadership at all study sites must be informed of vitamin C's effect on point of care (glucometer) blood glucose and arterial blood gas glucose point of care values.

◆ In-service training will be documented in the Study Training Log

◆ Bold signage will be displayed on all study instructions, data collection forms, and at the patient's head of bed, stating:

◆ STOP! Do not use Accuchek or other Point of Care devices to measure glucose on this patient

◆ Use only metabolic or gas lab glucose screening methods

◆ This patient is enrolled in a study with Vitamin C, which artefactually increases POC glucose testing

◆ Do Not Initiate or Utilize Sliding Scale, Scheduled Insulin, or Continuous Insulin Infusion Without Laboratory Confirmation of Blood Glucose

◆ Those receiving insulin infusion or sliding scale insulin will have metabolic glucose screening on the schedule determined by the primary physician and paid for by the study

◆ Blood glucose monitoring for insulin administration guidance should only be by a metabolic or blood gas laboratory measured blood glucose results, whether or not the study patient is receiving insulin

◆ Study personnel will follow each study patient closely to monitor insulin use to ensure that point of care glucose screening is suspended for the research subject.

◆ If subject loses central venous access (PICC line and arterial line acceptable), Vitamin C infusions are to stop but subject not

withdrawn. Data collected through end of study.

◆ Point of care glucose testing may resume 36 hours after the last infusion of study drug.

3. If the disclosure of any of the information obtained during the study would place the individual at risk for harm (legal, reputation, emotional etc.) and the information will be recorded so that the individual could be identified, explain the protections that will be put in place to decrease the risk of disclosure:

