4. * The Code of Virginia requires that most medical personnel and all employees of institutions of higher education report suspected child/elder abuse or neglect. Is it likely investigators could discover information that would require mandatory reporting by the investigators or staff:

Yes
 No

5. * Is it likely investigators could discover a participant's previously unknown condition (eg disease, suicidal thoughts, wrong paternity) or if a participant is engaging in illegal activities:

Yes
 No

6. If yes, explain how and when such a discovery will be handled:

7. * Describe any potential risks or harms to a community or a specific population based on study findings:

N/A

8. * Describe criteria for withdrawing an individual participant from the study; such as safety or toxicity concerns, emotional distress, inability to comply with the protocol, etc.:

Patients may withdraw from the study at any time. The investigators can withdraw any patient at any time from the study if medically necessary. If for any reason the study treatment or observations were discontinued the reasons will be recorded and the DSMB will be informed.

9. * Summarize any pre-specified criteria for stopping or changing the study protocol due to safety concerns:

The study protocol will be stopped in the event that any participant develops an adverse event or side effect which is known to be associated with the vitamin C infusions, or if patients develop exclusion criteria after enrolment.

10. Where appropriate, discuss provisions for ensuring necessary medical, professional, or psychological intervention in the event of adverse events to the subjects:

Investigators will determine daily if any clinical adverse experiences occur during the period from informed consent through study hour 24 and will be followed up through resolution, resolved with sequelae, unresolvable or death.

It is expected that Diseases/Illnesses/Symptoms associated with the study population will occur in the study population, independent of investigation product exposure. These associated diseases/illnesses/symptoms will be considered as part of the study inclusion processes and/or study assessments and as such will not be considered ◆reportable◆ Adverse Events (AE)/Serious Adverse Events (SAE) unless the Investigator has a reasonable doubt regarding the relatedness of the event to the investigational product.

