The investigator will evaluate any changes in laboratory values and physical signs and will determine if the change is clinically important and different from what is expected in the course of treatment of the study patients. If clinically important and unexpected adverse experiences occur, they will be recorded on the adverse event case report form.

The following will be considered reportable adverse events:

For this trial, a reportable adverse event is defined as:

1. Any clinically important untoward medical occurrence in a patient receiving study drug or undergoing study procedures which is different from what is expected in the clinical course of a patient undergoing AF ablation, or,
2. Any clinically important, untoward medical occurrence that is thought to be associated with the study drug or procedures, regardless of the ◆expectedness◆ of the event for the course of a patient undergoing cardiac bypass surgery.
3. Investigators will report all serious, unexpected, AND study-related adverse events from the time of informed consent through study hour 48 that are considered to be harmful and unintended responses to the investigational product and/or study related procedures in the participants◆ case report forms. ◆Responses to investigational product◆ means that the causal relationship between an investigational product and an adverse event cannot be ruled out.

The following will be reported as adverse events:

Investigators will report all unanticipated problems that involve risk or harm to a research participant AND was not anticipated or foreseen (e.g., not described in the consent form) AND is probably or definitely related to or caused by the research to the sponsor/IND Holder by phone and email within 24 hours of becoming aware of event. The Institutional Review Board will be notified within 5 business days of receiving notice of the unanticipated problem.

Investigators must report Unanticipated Problems to the sponsor, regardless of severity, associated with the study drug or study procedures within 24 hours. An unanticipated problem is defined as follows:

Any incident, experience, or outcome that meets all of the following criteria will be reported from the time of consent through study hour 48 until resolved, withdrawn from the study, death occurs or lost to follow up:

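### Item 9 stops the whole study for one recognised vitamin C side effect of any severity in either blinded arm; a participant-level stop was probably meant, and the wording should be corrected

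*Protocol*

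**What the plan says.** The form's prompt at item 9 of Risks, Discomforts, Potential Harms and Benefits is "Summarize any pre-specified criteria for stopping or changing the study protocol due to safety concerns". The answer is that the study protocol is "stopped in the event that any participant develops an adverse event or side effect which is known to be associated with the vitamin C infusions". A second limb adds a further trigger: "or if patients develop exclusion criteria after enrolment". Nothing else is said there: no grade, no causality judgement, no number of events, no arm and no mention of the DSMB.

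The neighbouring text bears on how this is read:

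- **Item 1 of the same section** names, from patients with advanced cancer, "infrequent side effects consisting of nausea, vomiting, dizziness, and headache".
- **Item 2** covers loss of central venous access: "Vitamin C infusions are to stop but subject not" withdrawn, and data collection goes on.
- **Item 8** deals separately with withdrawal of individuals and adds: "If for any reason the study treatment or observations were discontinued the reasons will be recorded and the DSMB will be informed".
- **Item 10**, second definition of a reportable event, uses a narrower test: "Any clinically important, untoward medical occurrence that is thought to be associated with the study drug or procedures".
- **Research Description, item 4**, handles an early reaction patient by patient: "Once the subject has demonstrated no adverse effects of the first infusion, the AF ablation will proceed as scheduled".
- **DSMB Details, items 2 and 3**, set six-monthly meetings, with an earlier one for unanticipated serious events. Two or more of the three members may vote to request a halt to the study or to interrupt treatment of individual patients.

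**The concern.** A study-level stopping rule should respond to evidence of harm. This one responds to the type of an event. Whether an effect is recognised for vitamin C does not depend on how bad it was, whether vitamin C caused it in this patient, or whether the patient received vitamin C at all. The trial is double-blind and the rule speaks of any participant, so a symptom on placebo after an ablation counts in the same way.

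Safety is one of the primary endpoints (Research Description, item 2), and the sample-size rationale rests on completing 20 patients (Study Population, item 3). A stop after one mild symptom would leave both the safety question and the biomarker question unanswered. If instead only the affected participant's infusions were meant to stop, the item says something its authors did not intend, and staff cannot tell from it which action to take.

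**Working it through.** The plan gives no trigger probability or other figure for this rule, so there is nothing to reproduce. The point rests first on the text.

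**Step 1: what level does item 9 address?** The prompt and the first limb of the answer both name the study protocol, and item 8, directly above, already covers individual withdrawal. That favours a study-level reading. The second limb makes little sense at study level, because one patient acquiring an exclusion condition is no reason to close the trial. The first-infusion check, the venous-access rule and the DSMB's power over single patients all work per participant. That favours a participant-level reading. The text does not settle the matter, though the second is the more probable intention.

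**Step 2: does other text narrow the trigger?** Item 10 filters events by clinical importance, unexpectedness and doubt about relatedness, but for recording and reporting. Item 9 does not refer to those filters. One of them points the other way: the adverse event form takes events that are clinically important and unexpected, whereas item 9 acts on effects already recognised.

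**Step 3: does the DSMB text supply the missing condition?** Item 8 means that the DSMB learns of any discontinuation, and DSMB Details gives it a halting vote. Neither limits the automatic stop in item 9. The early-meeting trigger is for unanticipated serious events, so by its words a serious event of a recognised type does not call an early meeting.

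**Step 4: size under the literal reading only.** Inputs: n = 20 (Study Population, item 3), and an assumed per-patient rate q of a qualifying event, the same in both arms. The documents give no rate for the listed symptoms, so q is hypothetical.

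Probability of at least one event: P = 1 − (1 − q)^20. Mean number enrolled by the trigger or completion, if patients are treated one after another: P / q.

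| Assumed q | P(rule triggers) | Mean enrolled of 20 |
|---|---|---|
| 1% | 1 − 0.99^20 = 18% | 0.1821 / 0.01 = 18.2 |
| 2% | 1 − 0.98^20 = 33% | 0.3324 / 0.02 = 16.6 |
| 5% | 1 − 0.95^20 = 64% | 0.6415 / 0.05 = 12.8 |
| 10% | 1 − 0.90^20 = 88% | 0.8784 / 0.10 = 8.8 |

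The probability reaches one half at q = 1 − 0.5^(1/20) = 3.4%.

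The 1–10% that item 1 gives for hyperoxaluria is not the source of this range. The sample schedule describes blood draws only and no urine oxalate test, so hyperoxaluria would probably not be detected as an event.

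**The case against.** The strongest case on the other side is that item 9 is a loosely worded participant-level rule and that little is missing once it is read so. The second limb fits only that reading, and the rest of the protocol handles events per patient. Study-level control exists: an independent three-member board that can unblind and can request a halt by two votes, and that item 8 tells of every discontinuation. The prompt asks for any criteria there may be and does not demand a numerical boundary. Leaving the halt to board judgement is a reasonable choice in a single-centre pilot with 24 hours of dosing.

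Most of this stands. The participant-level intention is probable, the DSMB is informed, and no count rule is required. The evidence on rates is also fair. The protocol calls the listed symptoms infrequent, and it reports no significant adverse effects in the stenting trials and no serious adverse events in the sepsis trial.

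What does not stand is that the wording can therefore be left alone. A mandatory instruction to stop the study protocol is not cured by a discretionary power elsewhere, nor by reporting filters that it does not cite.

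Two stronger inferences are tempting. A reader might conclude from the table that the trial will probably be stopped early. The documents do not support this, because the rates are assumed and the table applies only if staff follow the literal text. A reader might also conclude that the trial has no study-level safeguard. It has one in the DSMB vote; what it lacks is a correctly stated criterion in the field that asks for one.

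**Conclusion.** The rule as written is wrong and should be corrected. Taken literally, a single mild recognised symptom in either arm ends the study without showing harm. Taken as probably intended, the answer is misworded for its field, and study-level halting rests on the DSMB's discretion. The wording needs correction on both readings.

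This conclusion depends on the text and not on any event rate. The range of 18% to 88% assumes rates of 1% to 10%, equal in the two arms, with all 20 patients at risk. It shows only how sensitive a one-event rule is and does not set the seriousness of the point. The documents give no basis for a particular event count or severity grade as a threshold, so none is proposed here.

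**What to change.** Reword item 9 in two parts, using terms the protocol already has.

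1. **Participant level.** Stop a participant's remaining infusions, with follow-up and data collection continuing as in the venous-access rule, for either of two reasons: an event that is clinically important and thought by the blinded investigator to be associated with study drug (the test in item 10's second definition), or a newly developed exclusion condition that makes further dosing unsafe. Inform the DSMB, as item 8 provides.
2. **Study level.** Pause or stop the study only through the DSMB vote in DSMB Details, item 3. Require prompt DSMB review of any serious event judged related to study drug, whether anticipated or not. Leave to the DSMB whether a number of lesser events should also prompt review. If it sets one, the trigger probability for that number should be stated.

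The cost is one amended item, with IRB and DSMB acknowledgement, and no extra patients or procedures. The downside is a less automatic study-level stop in a population where the protocol calls this the first such trial. Prompt review of serious related events and notice to the DSMB of every discontinuation limit that loss.

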View: SF - Communication Plan for Research Team

Communication Plan for Research Team

1. * Describe the process that will be used to ensure that all persons at all involved sites assisting with the research are adequately informed about the protocol and their research related duties and functions:

VCU will be the only site for the study. All study personnel have completed CITI training. All study personnel will meet with the PI prior to the initiation of the study and every 6 months thereafter during study progress meetings. Additional training will be conducted as needed in response to any changes in the study protocol. Study personnel will be instructed to call and/or page the PI [name] directly with any adverse events or other problems with the study conduct.

IRB Panel Setup

1. * To which IRB is this study being submitted for review:

VCU IRB
 Western IRB
 NCI Central IRB
 Other IRB

2. If Other IRB, name the IRB that will review this research. If ORSP has not already agreed to rely on this IRB (via phone or email communication), you are strongly advised to contact [contact] before proceeding with this submission:

Review Setup

1. * Does this study involve greater than minimal risk:

Yes
 No

2. * Review Type Requested: (subject to IRB approval)

Full Board
 Expedited
 Exempt

3. * Has this protocol received a Massey protocol review:

Yes
 No

4. * Has this human subjects protocol (not the grant application) been reviewed by the funder:

Yes
 No

Research Description

1. * Describe the study hypothesis and/or research questions. Use lay language whenever possible.

Treatment with intravenous (IV) vitamin C in patients who are undergoing a non-invasive catheter ablation procedure to treat their atrial fibrillation (AF, a form of irregular heart beat) will be safe, well tolerated, and may lead to a reduced level of inflammation after the procedure.

2. * Describe the study's specific aims or goals. Use lay language whenever possible.

This will be a double-blinded, placebo-controlled pilot study to measure the effects of IV vitamin C in patients who are being scheduled for AF ablation (N=20). The primary endpoints will be evaluation of the safety of the IV vitamin C infusion and it's efficacy in reduction of inflammatory markers in the blood of patients undergoing AF ablation.

3. * Describe the study's background and significance, including citations, or upload a citation list in document upload. Use lay language whenever possible.

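### The adverse event rules disagree on causality, on which events reach the AE form, and on a time window with no stated hour 0, although infusion safety is a primary endpoint

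*Protocol*

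**What the plan says.** Research Description, item 2 of the protocol sets the aim: "The primary endpoints will be evaluation of the safety of the IV vitamin C infusion", alongside reduction of inflammatory markers, with N=20.

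The adverse event rules stand in Risks, Discomforts, Potential Harms and Benefits, item 10:

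- **Daily check.** "Investigators will determine daily if any clinical adverse experiences occur during the period from informed consent through study hour 24".
- **Conditions that go with the study population.** These are not reportable "unless the Investigator has a reasonable doubt regarding the relatedness of the event to the investigational product".
- **Laboratory and physical changes.** "The investigator will evaluate any changes in laboratory values and physical signs", judging clinical importance and departure from the expected course of the study patients. No window is given.
- **AE form.** "If clinically important and unexpected adverse experiences occur, they will be recorded on the adverse event case report form".
- **Reportable event 1.** A clinically important occurrence that differs from the expected course of an ablation patient.
- **Reportable event 2.** Expectedness does not count here; the sentence begins "Any clinically important, untoward medical occurrence that is thought to be associated with the study drug or procedures, regardless of the" and goes on to name the event's expectedness.
- **Reportable event 3.** "Investigators will report all serious, unexpected, AND study-related adverse events from the time of informed consent through study hour 48", entered in the case report forms.
- **Unanticipated problems, first paragraph.** Report to the sponsor within 24 hours if, among other conditions, the relation to the research is probable or definite.
- **Unanticipated problems, definition that follows.** Also a 24-hour sponsor report. An incident that meets all criteria "will be reported from the time of consent through study hour 48 until resolved" or another listed end point; the relatedness criterion is met by a possible relation.

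Elsewhere, Research Description, item 4 has the team record documented adverse events from the charts for 12 months, with calls at 3 and 12 months. Sample Collection, item 3 times the 24-hour laboratory draw from the start of the first infusion.

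**The concern.** When safety is a primary endpoint, the adverse event record is endpoint data. Its content should not depend on which sentence of one section a staff member follows. Here it can in three ways: a possibly related problem may or may not trigger the sponsor report; an expected but drug-associated event is reportable but has no stated place on the form; and the two time limits cannot be placed on the clock.

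DSMB Details, item 3 lists adverse events among the data the board receives, so the same uncertainty reaches safety oversight. An analysis plan can define how recorded events are tabulated, but it cannot recover an event that was not recorded.

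**Working it through.** The plan gives no figure to reproduce. The check sets the rules side by side and then does the timing arithmetic.

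**1. Causality threshold for the 24-hour report of unanticipated problems**

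| Judged relation | First paragraph | Definition that follows |
|---|---|---|
| Possible | out | in |
| Probable | in | in |
| Definite | in | in |

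The two texts govern the same report to the same recipient within the same time. They contradict each other for possibly related problems and agree otherwise.

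**2. AE form against reportable events** (clinically important, non-serious; expectedness judged against the ablation course)

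| Expected after ablation? | Thought associated with drug or procedures? | Reportable (1 or 2) | AE form sentence |
|---|---|---|---|
| yes | no | no | no |
| yes | yes | **yes** | **not provided for** |
| no | no | yes | yes |
| no | yes | yes | yes |

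Three of the four combinations are reportable and two have a stated entry to the form. The mismatch is one cell, and it is the one that reportable event 2 adds. Reportable event 3, the only other sentence in the text available that names a case report form, does not fill it, because it too requires the event to be unexpected.

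**3. Windows**

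Inputs: four infusions, 6 h apart, 0.5 h each, with a tolerance of 3 h (Research Description, item 4). Assumption: study hour 0 is the start of the first infusion.

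End of fourth infusion = start of fourth infusion + 0.5 h.

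| Timing | Fourth starts | Fourth ends | Hour 24 minus end | Hour 48 minus end |
|---|---|---|---|---|
| Nominal, 3 × 6 | 18 h | 18.5 h | 5.5 h | 29.5 h |
| 3 h late on the clock, 18 + 3 | 21 h | 21.5 h | 2.5 h | 26.5 h |
| 3 h late at each interval, 3 × 9 | 27 h | 27.5 h | −3.5 h | 20.5 h |

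The protocol does not say whether the tolerance applies to the clock or to each interval. On the last reading, daily determination stops before dosing does.

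- 24-hour kidney function draw: 24 − 12 = 12 h to 24 + 12 = 36 h, so up to 36 − 24 = 12 h after daily determination ends.
- 30-day safety labs: days 30 − 14 = 16 to 30 + 14 = 44 (day 0 taken as the first infusion). Hour 48 is day 2, so they fall 14 to 42 days after it.
- If hour 0 were consent, which is taken at a clinic visit before admission, both limits could pass before any infusion.

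**4. Weight of one event**

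1/20 = 0.05, or 5 percentage points of the overall rate in the planned sample.

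**The case against.** The case for leaving the text alone has substance.

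- **The form sentence does not say only.** It bars no entry, and the case report forms and their instructions are not in the text available. A reader might infer that expected drug-related events are excluded from the form; the document does not say so. This stands, and it is why the second part is a mismatch of scope and not a contradiction.
- **Expectedness is judged against the ablation course.** A known effect of the drug that is unusual after ablation still goes on the form. This stands and confines the gap to one cell.
- **Other capture exists.** The 12-month chart recording has no filter for expectedness, seriousness or attribution, and two calls are planned. Items 8 and 9 of the Risks section add that reasons for discontinuation are recorded and passed to the DSMB, and that known vitamin C effects bear on stopping. A reader might infer that adverse event collection ends at hour 24, or that events will be lost; the documents support neither. But the chart recording depends on what was documented, and none of these provisions names the AE form.
- **Recording is blinded.** Judgments are made without knowledge of arm, so a reader should not infer a bias between arms from these rules.
- **Hours 24 and 48 govern different activities, and the first infusion is the natural zero.** Different limits are therefore not in themselves a contradiction. The missing definition remains, and so does the reading on which dosing outlasts the daily check.
- **Unfiltered recording goes beyond reconciliation.** It does change the approach chosen in item 10, but it removes the mismatch at contacts that already exist.

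Nothing on this side answers the causality contradiction.

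**Conclusion.** The point holds in three parts of unequal strength. The causality threshold is a direct contradiction, limited to possibly related unanticipated problems and to expedited reporting. The form rule leaves one class of reportable events, those expected after ablation and thought associated with drug or procedures, without a stated entry to the AE form; the chart recording reduces that gap but does not close it. The windows lack a defined zero. If zero is the first infusion, the margin between the end of dosing and the end of daily determination runs from 5.5 h to −3.5 h, depending on how the tolerance is read.

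Under-recording is a risk, not a certainty. The number of events affected, and any effect on the comparison between arms, cannot be derived from the document. The 5 percentage points per event is a scale for a sample of 20, not an estimate of loss. The mention of cardiac bypass surgery in reportable event 2 is an editorial leftover and changes no event's reportability. The matter should be fixed, because it touches a primary endpoint and the remedy is cheap.

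**What to change.** Reconcile Research Description, item 4 with Risks, item 10:

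1. State one causality threshold for unanticipated problems and use it in both places.
2. Define study hour 0 once. Sample Collection, item 3 already offers an anchor for the labs.
3. Record adverse events on the case report form in both arms, whatever their expectedness or attribution, over one window that covers all infusions and the existing safety-lab contacts, for example through the 30-day visit. Keep the chart review and the 3- and 12-month calls.
4. Use the expectedness and relatedness filters for expedited reporting only.
5. Correct the cardiac bypass surgery wording.

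The cost is protocol and form wording, plus modest extra data entry for about 20 patients at contacts that already exist. No dose or treatment rule changes.
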